9.3.3 Procedure for the handling of discontinued subjects

9.3.3.1 Handling of subjects who discontinued from the trial

The principal investigator must document any discontinuation of a subject and inform the sponsor. Where applicable, the relevant IECs or IRBs must be informed with a detailed written explanation.

The following must be done for **all** discontinued subjects, including those who withdrew informed consent:

- Document the main reason for discontinuation from the trial.
- Ensure that all data collected until the time of discontinuation is transferred to the eCRF.
- Complete any other trial-related formalities, e.g., those related to discharge from the trial site.
- For subjects withdrawing consent, document in the source data the date and time of withdrawal.
- If possible, perform an Early Termination Visit, with procedures identical to Visit 17. Subjects who withdraw consent and agree to perform the Early Termination Visit must document their approval in writing.

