- Time-to-event variables: Kaplan-Meier estimates together with the 95% confidence intervals (CI) and the hazard rate will be provided with the respective number at risk and the number censored at the relevant time points. In addition, the median time-to-event and its 95% CI will be presented if applicable. For calculating the survival estimate CI bounds, the log-log transformed estimate of CI bounds will be used. The time to event will be censored at the Visit 11 for the Week 26 report and End-of-Treatment Visit/End-of-Trial Visit for the final report if not otherwise specified.

Medical terms (e.g., prior and concomitant diseases, adverse events) will be coded via Medical Dictionary for Regulatory Activities (MedDRA). For the analysis, the primary System Organ Class SOC will be used. Medications will be coded according to World Health Organization Drug Dictionary (WHO-DD).

Table 1 shows the use of analysis sets in different analyses as defined in Section 9.

Table 1: Use of analysis sets

	Enrolled Set	Allocated Set	SAF	FAS	PKS	PDS
Subject disposition	X	X	X	X		
Discontinuations	X	X	X	X		
Protocol deviations			X			
Demographics			X	X		
Other baseline characteristics			X	X		
Subject medical and dental history			X	X		
CRPS history			X	X		
Prior and concomitant medication			X	X		
Exposure			X			
Compliance			X			
Primary endpoint				X		
Secondary endpoint				X		
Adverse events			X			
Laboratory values			X			
Pharmacokinetic concentrations					X	
Bone turnover markers						X
Soluble interleukin-2 receptor (sIL-2R)			X			
Other safety parameter			X			

FAS = Full Analysis Set, PDS = Pharmacodynamic Set, PKS = Pharmacokinetic Set, SAF = Safety Analysis Set

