##### Duration of effect – Response based on duration of effect

The duration of effect for treatment period A is defined as the time from baseline to first loss of response. Response is defined as at least 30% decrease from baseline and first loss of response is

the first time after achieving response that a subject shows less than 10% decrease from baseline. Duration of effect is then the time from baseline till the last timepoint before first loss of response. Pain assessments (tablet computer) that are considered for this analysis are those at Day 1 (Baseline), Week 6, Week 12, Week 16, Week 22 and Week 26.

Subjects never reaching a 30% decrease from baseline will have a duration of effect of 0 weeks. Subjects reaching a 30% decrease from baseline but showing no loss of effect, i.e. not dropping to below 10% decrease from baseline afterwards, will be censored at Week 26 with a duration of effect of 26 weeks. Else the duration of effect is taken as the last assessment a subject shows an effect (at least 30% response) before first experiencing a loss of response. e.g., if subject shows less than 30% decrease at Week 6, at least 30% decrease at Weeks 12 and 16 and at Week 22 less than 10% decrease, the duration of effect is set to 16 weeks.

Duration of effect will be analyzed using survival analyses with timepoints respective to the visits where pain is assessed on the tablet computer. A frequency table for the duration of effect will be provided for Follow-Up Period 1.

Furthermore, to assess the effect of a second treatment cycle, for those subjects who received two treatment cycles of neridronic acid, descriptive statistics for the change in average pain intensity from baseline, the change in average pain intensity from Week 26 and pain response as % decrease from baseline and from week 26 will be displayed for Follow-up Period 2 for the following responder subgroups based on duration of effect.

- Never-responders: subjects with a duration of effect = 0 weeks.
- Lost-responders: Subjects with a duration of effect <26 weeks.
- Responders: subjects with a duration of effect =26 weeks.

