#### **19.1.1.9 Handling of data from early termination visits**

Subjects who discontinue the 52-week trial period before their Week 52 visit (Visit 17) are requested to undergo an Early Termination Visit with identical procedures to Visit 17. Data from the Early Termination Visit recorded under Visit 17 will not be included in the analysis of data from scheduled visits at Visit 17.

Instead data from the Early Termination Visit will be assigned to the nearest scheduled visit based on the study day of the early termination visit and the planned visit day. The planned visit day is

- Day 1 for Visit 2
- Day 4 for Visit 3
- Day 7 for Visit 4
- Day 10 for Visit 5
- Day 15 for Visit 6
- Day 43 for Visit 7
- Day 85 for Visit 8
- Day 113 for Visit 9
- Day 155 for Visit 10
- Day 183 for Visit 11
- Day 186 for Visit 12 (only if subject is retreated)
- Day 189 for Visit 13 (only if subject is retreated)
- Day 192 for Visit 14 (only if subject is retreated)
- Day 197 for Visit 15 (only if subject is retreated)
- Day 253 for Visit 16
- Day 365 for Visit 17

In case of equal distance to two scheduled visits the earlier visit will be chosen. If the assigned visit already occurred before the early termination visit, then the data will be assigned to the next

scheduled visit. Visits 12, 13, 14 and 15 are only applicable for subjects who have been treated in Treatment Period B.

Data from the Early Termination Visit will be analyzed using the re-assigned visits.

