#### **19.1.1.14 Kaplan-Meier analysis**

For Kaplan-Meier analyses in the 12-week trial period, the unit of time is days, the start time is the date/time of first IMP, and the censoring time is the day of Visit 8 or, in case of dropouts, the day of the Early discontinuation Visit 17.

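### SAP 13.3.2 gives 26 weeks of effect to every responder without an observed loss, early leavers included, which inflates the Week 26 result; its dating rule and data source also need settling

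*SAP*

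**What the plan says.** **Duration rule.** SAP 13.3.2 uses tablet ratings at Day 1 and Weeks 6, 12, 16, 22 and 26. Response is at least 30% decrease from baseline; loss is the first later rating with less than 10% decrease. A subject who never responds gets 0 weeks. A responder with no loss seen "will be censored at Week 26 with a duration of effect of 26 weeks". Remaining in the trial is not a condition.

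**Three statements of duration.** Duration first "is defined as the time from baseline to first loss of response". Next: "Duration of effect is then the time from baseline till the last timepoint before first loss of response". A later sentence, followed by a worked example, takes the last assessment with at least 30% response before the loss.

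**Other censoring rules.** SAP 8.1: "The time to event will be censored at the Visit 11 for the Week 26 report". The same sentence names the End-of-Treatment or End-of-Trial Visit for the final report, unless otherwise specified. SAP 19.1.1.14 has a dropout rule ("in case of dropouts, the day of the Early discontinuation Visit 17"), but its scope is "For Kaplan-Meier analyses in the 12-week trial period".

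**Early Termination.** SAP 19.1.1.9: "Data from the Early Termination Visit will be analyzed using the re-assigned visits". Protocol 9.3.3.1 makes that visit conditional: "If possible, perform an Early Termination Visit, with procedures identical to Visit 17".

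**Data source.** Protocol 1.2 bases duration of effect on average pain in the electronic diary, which Protocol 12.3.1.1 makes weekly after Visit 8. SAP 3 names the protocol of 14 Mar 2018. SAP 13.3.3 refers diary analysis back to SAP 13.1.1, where diary data after Day 84 are only listed.

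**The concern.** A responder who leaves after Week 6 has been observed for 6 weeks, yet is held in the risk set and tabulated as having 26 weeks of effect. Any loss after departure cannot be seen, so such subjects only push the Week 26 figure up, and push it further in an arm that loses more subjects after response. SAP 13.2.2 goes the other way: there, a missing Week 26 score makes the subject a non-responder.

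The derivation is also not unique. Two programmers could follow different sentences and obtain different durations for a subject whose relief passes through the 10% to 30% band before loss. The lost-responder group, defined only as under 26 weeks, also takes in the never-responders at 0 weeks.

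Finally, an outcome that the current protocol defines on the diary has no diary analysis in the SAP. From Week 12 to Week 26 the tablet gives 3 ratings (Weeks 16, 22 and 26), while the weekly diary gives up to 26 − 12 = 14.

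**Working it through.** **1. The SAP's own example.** Below 30% at Week 6, at least 30% at Weeks 12 and 16, below 10% at Week 22; stated result 16 weeks. The second and third sentences both give 16. The first gives 22, so the example rules the first out as the computing rule.

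**2. Where the second and third sentences part.** Relief of 35%, 20% and 5% at Weeks 6, 12 and 16: the second gives 12 weeks, the third 6. The example cannot decide between them.

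**3. One early leaver.** Response at Week 6, then departure without a further rating: 26 weeks under the SAP; last observed at 6 weeks.

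**4. Week 26 proportion.** The documents give no loss or dropout rates, so these are assumptions: responders from Week 6; a fraction p = 0.4 lose response and a fraction d leave, independently, at times uniform over Weeks 6 to 26; visits at Weeks 12, 16, 22 and 26; every rating before loss at least 30%; no Early Termination ratings.

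Loss first seen at visit v = p × (gap/20) × (1 − d(v − 6)/20), with gaps of 6, 4, 6 and 4 weeks.

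| Visit | d = 0.1 | d = 0.2 |
|---|---|---|
| 12 | 0.12 × 0.97 = 0.1164 | 0.12 × 0.94 = 0.1128 |
| 16 | 0.08 × 0.95 = 0.0760 | 0.08 × 0.90 = 0.0720 |
| 22 | 0.12 × 0.92 = 0.1104 | 0.12 × 0.84 = 0.1008 |
| 26 | 0.08 × 0.90 = 0.0720 | 0.08 × 0.80 = 0.0640 |
| Seen losses | 0.3748 | 0.3496 |
| Shown at 26 weeks | 0.6252 | 0.6504 |

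The truth is 0.60. Subjects rated at Week 26 without loss number 0.6(1 − d), so the share of the 26-week subjects who had left is 1 − 0.54/0.6252 = 13.6% and 1 − 0.48/0.6504 = 26.2%.

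**5. The rest of the curve.** Losses are backdated to the previous visit. At d = 0.1 the SAP curve reads 80.8%, 69.7% and 62.5% at Weeks 12, 16 and 22; the true values are 88%, 80% and 68%. Its last crossing of the true line is at 6 + 0.3748/0.02 = Week 24.7 (d = 0.2: 6 + 0.3496/0.02 = Week 23.5). Before that it is below the truth at every visit. Only the flat step just before a visit can run slightly above the falling true line, by at most 69.7 − 68 = 1.7 points at d = 0.1 and 71.4 − 68 = 3.4 at d = 0.2.

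Mean duration to Week 26:
- True: 0.6 × 26 + 0.4 × 16 = 22.0 weeks.
- SAP, d = 0.1: 0.1164 × 6 + 0.076 × 12 + 0.1104 × 16 + 0.072 × 22 + 0.6252 × 26 = 21.2.
- SAP, d = 0.2: the same sum gives 21.5.

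**6. Censoring at the last assessment.** With loss dated where first seen, the dropout factor cancels at each visit and the curve is 88%, 80%, 68% and 60%, exact at the visits. Its mean is 12 + 4 × 0.88 + 6 × 0.80 + 4 × 0.68 = 23.0 weeks, too long. With loss backdated, Week 26 gives 60.9% and 61.9%, so 35% to 37% of the excess remains.

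**7. Sensitivity** (simulation where Early Termination ratings or informative dropout enter).
- Every dropout rated at Early Termination: SAP 62.0% and 63.9%; detection-dated 60.4% and 60.8%.
- Over 20% to 60% loss and 10% to 30% dropout, with or without those ratings: SAP excess at Week 26 of 1.0 to 11.3 points; detection-dated 0 to 1.8.
- Over the same loss and dropout rates, without those ratings, the SAP mean is 0.1 to 1.2 weeks too short and the detection-dated mean 0.5 to 1.6 weeks too long.
- 10% dropout plus a quarter of those losing response leaving unrated: SAP 72.0%, detection-dated 67.8%, truth 60%.

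**8. Size in the trial.** With 90 per arm and half responding (assumed): 45 × 0.0252 = 1.1 and 45 × 0.0504 = 2.3 subjects, or 1.3 to 2.5 points of the arm. The sampling SE at 30% is √(0.3 × 0.7/90) = 4.8 points.

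**The case against.** The best reply is that the rule does not lengthen duration overall. This stands: backdating outweighs the dropout error, so the mean is too short and the curve is low at the visits before Week 26. Dating loss at detection is no general cure either, because it misses the mean by more.

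The first duration sentence can fairly be read as the concept and the second as its operational form. That also stands, and leaves the second against the third as the live conflict.

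SAP 8.1 does name an End-of-Trial Visit, but only for the final report and only where nothing else is specified; SAP 13.3.2 specifies something else. For the Week 26 report SAP 8.1 points to Visit 11, which a dropout does not have. Early Termination ratings help, since a loss rated there counts. They do not move the censoring time of a subject without loss, and the visit may not take place.

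On data source, a reader might infer that the SAP carried over an outdated protocol definition. The documents do not support that: Amendment 01 added the outcome, so the tablet definition is the SAP's own. The conflict is with the current text of Protocol 1.2. Whether a later SAP exists cannot be seen from these documents.

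**Conclusion.** The point holds, at minor severity. As written, SAP 13.3.2 inflates the Week 26 proportion and the 26-week table row by 2.5 to 5.0 points among responders in the base case. That rests on assumed rates and is smaller than sampling error. The conflicting sentences, the overlapping group and the missing diary analysis follow from the text without any assumption.

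Three stronger readings are tempting and not supported:
- That the rule overstates how long relief lasts in general. Only the late end of the curve and the 26-week row are inflated.
- That dropout biases the second-course subgroups. Those subjects reached Visit 11; they carry only the overlapping labels.
- That efficacy conclusions are at risk. Protocol 1.2 places duration of effect among data not considered an endpoint, and no confirmatory test uses it.

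**What to change.** In one SAP amendment:

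- Censor responders without observed loss at their last pain assessment, Early Termination rating included. Show those censored before Week 26 in a separate row of the frequency table. State that this does not remove bias from informative dropout.
- Use one stated rule for dating loss in both curve and table, and align the worked example with it. Say that loss is known only to lie between two visits: backdating shortens duration, while dating at detection lengthens it but is unbiased at the visit times under non-informative dropout. An interval-censored estimate avoids the choice.
- Define lost-responders as more than 0 and less than 26 weeks, and count a loss first seen at Week 26 as lost.
- Update SAP 3 to the protocol including Amendment 01. Derive duration of effect from the diary, stating how the weekly means up to Week 12 and the single weekly ratings afterwards are combined. Keep the tablet version as supportive. Limit the Day 84 sentence in SAP 13.1.1 to the primary endpoint.

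The cost is the amendment and reprogramming of one exploratory outcome, plus a decision on how to join the two kinds of diary value. No protocol change or new data collection is needed.

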Use of a placebo control is considered justifiable when there are no established effective treatments for a disease or condition (ICH E10). As reflected in a recent Cochrane review of interventions for CRPS, there is no consensus for optimal management of this condition and the limited number of published trials provides only low or very low quality of clinical evidence for any intervention (O'Connell et al. 2013). In the absence of a suitable active comparator, the use of a placebo control allows for blinding and randomization to control for expectations of benefits that may occur from being in the trial. The placebo group also controls for spontaneous changes in the course of the disease. The use of placebo in this trial does not imply that subjects will be untreated, as subjects may continue to receive stable analgesic regimens during the trial as well as short-acting analgesics in case of severe pain flare related to CRPS (for details, see Section 1.4.2).

Trial design limitations

The concomitant use of pain medications in this trial, which are allowed because of the severity of the condition, may affect the sensitivity of subject-reported outcomes and the ability to detect changes in pain intensity. Therefore, it is important to emphasize the need for stable treatment during the trial at least until Week 12 to optimize assessment of the primary endpoint. Any changes in pain medications must be recorded.

Second treatment course

For those subjects not experiencing sufficient efficacy after a first treatment course with IMP as assessed at Visit 11 (Week 26), a second treatment period (Treatment Period B) in subjects with persistent pain is included to allow subjects previously on neridronic acid and on placebo to be treated with neridronic acid either for the second or the first time, respectively. The second treatment course is scheduled to occur after 26 weeks.

Subjects treated during Treatment Period B will provide data on safety and tolerability of a second treatment course as well as descriptive data on the efficacy of a second treatment course in subjects with no or insufficient response to the first treatment course as well as in subjects who lost response to the initial treatment course. Furthermore, subjects from the placebo group can receive verum treatment in Treatment Period B.

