#### 13.3.1 Pain Intensity recording on the tablet computer.

Analysis will be performed by descriptively summarizing average, worst and current pain intensity recorded on the tablet computer by visit and treatment group. In addition, changes from baseline and changes from Week 26 will be displayed. The value at Visit 2 is considered as baseline value.

Graphical display of the worst and current pain recording by visit and treatment will be done in addition to the primary endpoint graphical display of the average pain intensity recordings.

In addition, analysis will be repeated for subgroups defined by subjects who are treated in Treatment Period B in combination with the responder definition based on duration of response as defined in Section 13.3.2.

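### SAP 13.3.2 sets no lower bound for Lost-responders, so programmed as written that subgroup also takes in every never-responder

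*SAP*

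**What the plan says.** SAP 13.3.2, under duration of effect, works from average pain recorded on the site tablet. Response is a fall of at least 30% from baseline. Loss is the first assessment after a response at which the fall is under 10%. The assessments that count are "those at Day 1 (Baseline), Week 6, Week 12, Week 16, Week 22 and Week 26". Durations are then assigned by three cases:

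- No response at any time: "Subjects never reaching a 30% decrease from baseline will have a duration of effect of 0 weeks".
- Response with no later loss: subjects "not dropping to below 10% decrease from baseline afterwards, will be censored at Week 26 with a duration of effect of 26 weeks".
- All others: the last assessment with at least a 30% fall before the first loss. A worked example gives 16 weeks.

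For subjects given neridronic acid in both periods, second-course results are to be shown in three subgroups defined on duration alone:

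- The first subgroup takes only the value zero: "Never-responders: subjects with a duration of effect = 0 weeks".
- The second, which is the one at issue here, has an upper limit only: "Lost-responders: Subjects with a duration of effect <26 weeks".
- The third takes only the maximum value, and so holds the censored subjects: "Responders: subjects with a duration of effect =26 weeks".

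The SAP does not say that these groups are mutually exclusive or that they are assigned in sequence. SAP 13.3.1 reuses them: the tablet pain summaries are repeated for subjects treated in Period B "in combination with the responder definition based on duration of response as defined in Section 13.3.2". Protocol 8.1 gives the clinical background. Period B is to yield descriptive data in subjects with absent or insufficient response, and also "in subjects who lost response to the initial treatment course".

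**The concern.** The middle subgroup has an upper limit but no lower one. Never-responders carry a duration of 0 weeks, and 0 satisfies the condition of being below 26. A table programmed from the text would therefore count each never-responder twice, once under the correct label and once among subjects said to have lost a response.

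The display at stake describes how subjects do on a second course after losing an initial response. If it also holds subjects who never responded, its mean, median, quartiles and responder percentages describe a mixed group under a label that says otherwise. A reader who does not notice that the subgroup sizes overlap would take the mixed figure for the effect of retreatment after loss of response.

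**Working it through.** **Step 1. Reproduce the SAP's worked example.** Under 30% at Week 6, at least 30% at Weeks 12 and 16, under 10% at Week 22. The last assessment with response before the first loss is Week 16, so the duration is 16 weeks, as the SAP states.

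**Step 2. List every duration the rule can produce.** Class each of the five post-baseline assessments (Weeks 6, 12, 16, 22, 26) as at least 30%, 10% to under 30%, or under 10%. That gives 3^5 = 243 complete patterns. Applying the duration rule to each:

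| Duration (weeks) | 0 | 6 | 12 | 16 | 22 | 26 |
|---|---|---|---|---|---|---|
| Patterns | 32 | 40 | 39 | 32 | 20 | 80 |

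These are counts of possible patterns, not expected numbers of subjects. A subject who truly lost a response has a duration of at least 6 weeks. A duration of 0 can only mean that response was never reached.

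**Step 3. Apply the subgroup definitions.**

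| Subgroup | As written | With a lower bound above 0 |
|---|---|---|
| Never-responders | {0}: 32 patterns | {0}: 32 |
| Lost-responders | {0, 6, 12, 16, 22}: 32 + 40 + 39 + 32 + 20 = 163 | {6, 12, 16, 22}: 131 |
| Responders | {26}: 80 | {26}: 80 |
| Sum over groups | 32 + 163 + 80 = 275 for 243 patterns | 32 + 131 + 80 = 243 |

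As written, all 32 never-responder patterns fall in two groups. With the lower bound, each pattern falls in exactly one. The other two groups are the same either way.

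**Step 4. Size of the distortion.** Let f be the share of never-responders in the Lost-responder group as written, and let m1 and m0 be the mean falls in pain after the second course in true lost-responders and in never-responders. Then

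mean shown = f × m0 + (1 − f) × m1 = m1 − f × (m1 − m0).

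The documents give none of these quantities. Assume m1 = 2.0 points and vary the other two:

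| f | m0 = 2.0 | m0 = 1.5 | m0 = 0.5 |
|---|---|---|---|
| 25% | 2.00 | 1.88 | 1.63 |
| 50% | 2.00 | 1.75 | 1.25 |
| 69% (18 of 26) | 2.00 | 1.65 | 0.96 |
| 75% | 2.00 | 1.63 | 0.88 |
| 80% | 2.00 | 1.60 | 0.80 |

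The 69% row comes from an assumed split of 30 twice-treated subjects into 18 never, 8 lost and 4 responders. The group as written has 18 + 8 = 26 subjects, 18/26 = 69%, the three groups total 18 + 26 + 4 = 48, and the mean shown with m0 = 0.5 is (18 × 0.5 + 8 × 2.0)/26 = 25/26 = 0.96.

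**Step 5. Can the intended figure be recovered?** For the mean, yes, because the Never-responder row is clean. In the same example, (26 × 0.9615 − 18 × 0.5)/8 = (25 − 9)/8 = 2.0. Responder counts subtract in the same way. The medians and quartiles that SAP 8.1 also requires do not.

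**The case against.** The strongest reply is that the intended meaning is plain from the same subsection. Loss is defined as something that can happen only after a response, durations are assigned by successive exclusive cases, and the three labels follow those cases. A never-responder cannot have lost a response, so a careful programmer would allocate that group first and no mixing would occur. Even on the literal reading the error runs one way, the mean can be recovered by subtraction, and group sizes that add to more than the number retreated would be visible at table review. The output is a descriptive display of other efficacy data from an open-label period.

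Most of this stands. It shows what was meant and limits the consequences. It does not cure the definition, because the subgroup is set on duration alone and the text gives no order of assignment. Elsewhere the SAP spells out complementary groups, as for 30% and 50% responders and non-responders. Here it does not.

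Two stronger readings should be set aside. A reader might infer that second-course effects in never-responders and in lost-responders could not be told apart. They could, since the Never-responder display is correct and the mean for the other group follows by subtraction. A reader might also infer that the protocol requires these two kinds of subject to be described separately. Protocol 8.1 names both but does not say so. The separate descriptions in protocol 1.2 and 1.5.3 concern subjects treated or not treated in Period B, with a further split by initial treatment. Nor do the SAP groups map directly onto 8.1. A subject who reached 30% and never fell below 10% is a Responder in the SAP, yet may enter Period B with a score of at least 4 on the Week 26 PROMIS pain question.

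**Conclusion.** The point holds as a conditional one: if SAP 13.3.2 is programmed as written, the Lost-responder subgroup contains all never-responders, and its descriptive results in 13.3.1 and 13.3.2 are mixed. That much rests only on the SAP's own rule and on 0 being below 26. Whether the mixing occurs depends on how the tables are programmed.

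The size is unknown. The shift in the mean is the never-responder share times the difference in mean change between the two kinds of subject. It is zero if they respond alike, and large only if the share and the difference are both large. A reader might infer that the subgroup would consist mainly of never-responders. The Week 26 pain threshold for entering Period B makes a sizeable share plausible, but the documents give no counts, and the shares of 25% to 80% above are assumptions.

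No primary or secondary endpoint, confirmatory test, error rate or safety output is affected.

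**What to change.** In SAP 13.3.2, define Lost-responders as subjects with a duration of effect greater than 0 and less than 26 weeks, and add that the three subgroups are mutually exclusive. State in 13.3.1 that the same definitions apply there. This costs a few words and needs no new data or extra analysis. It is best settled before the tables are programmed.
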